#### **9.5.3.1 Additional Sample Collection for Future Use**

Optional blood samples for PBMC, RNA isolation and serum will be collected from each consenting subject prior to the first dose of MTX at Week -6, prior to the infusion on Day 1 and Weeks, 6, 14, 24, 36 and the End of Pegloticase Infusions Visit (if applicable) and the Week 52/End-of-Study/Early Termination. During visits at Weeks 2, 4, 8, 10 and 12, optional samples will only be collected if subjects are experiencing an acute gout flare on the day of visit.

Subjects may still participate in the study even if they decline to provide consent for the optional future use blood samples.

Samples will be retained for potential future analyses which may include biomarkers relevant to gout (e.g. inflammatory markers) or gout co-morbidities in response to pegloticase or other potential treatments for gout.

The samples will be retained no longer than 15 years after study completion or as required by applicable law. The samples will be stored in a secured storage space with adequate measures to protect confidentiality.

Detailed instructions regarding blood sample timing and handling are provided in the Laboratory Manual.

## 9.5.4 Safety Variables

Safety will be assessed via AE and concomitant medication use monitoring, physical examinations, vital signs, clinical safety laboratory evaluations (complete blood count, chemistry, urine albumin:creatinine ratio), pregnancy testing (if applicable), electrocardiograms (ECGs), and AEs of special interest (i.e., IRs, anaphylaxis, gout flares, and cardiovascular events).

### 9.5.4.1 Adverse Events

#### 9.5.4.1.1 Definitions

##### 9.5.4.1.1.1 Adverse Event Definition

As defined by the ICH, an AE is any untoward medical occurrence in a clinical study subject administered a medicinal (investigational or non-investigational) product, whether or not the event is considered related to the study drug. An AE is therefore any unfavorable and unintended sign (including an abnormal laboratory finding), symptom, or disease (new or exacerbated) temporally associated with the use of the study drug. This includes any occurrence that is new in onset or aggravated in severity or frequency from the baseline condition, or abnormal results of diagnostic procedures, including laboratory test abnormalities.

Examples of an AE include:

- Conditions newly detected or diagnosed after the signing of the ICF, including conditions that may have been present but undetected prior to the start of the study
- Conditions known to have been present prior to the start of the study that worsen after the signing of the ICF
- Signs, symptoms, or the clinical sequelae of a suspected drug interaction
- Signs, symptoms, or the clinical sequelae of a suspected overdose of either investigational product or a concomitant medication (overdose per se should not be reported as an AE)

Issues that will not be considered an AE include:

- Conditions present at the start of the study, should be recorded as medical history
- Medical or surgical procedures (e.g., endoscopy, appendectomy; however, a condition that leads to a procedure is an AE if it qualifies according to the definitions above)
- Situations where an untoward medical occurrence did not occur (e.g., social, diagnostic, elective, or convenience admission to a hospital)
- Fluctuations of pre-existing disease(s) or condition(s) present or detected at the start of the study that do not represent a clinically significant change from baseline
- Abnormal laboratory or test findings that are not assessed by the Investigator as a clinically significant change from baseline

AEs are divided into the categories “serious” and “non-serious.” This determines the procedures that must be used to report/document the AE.

#### 9.5.4.1.1.2 Serious Adverse Event Definition

Based on ICH guidelines, an SAE is any untoward medical occurrence that at any dose:

- Results in death
- Is life threatening

NOTE: The term 'life threatening' in the definition of 'serious' refers to an event in which the subject was at risk of death at the time of the event. It does not refer to an event that hypothetically might have caused death if it were more severe, prolonged, or untreated.

- Requires hospitalization or prolongation of existing hospitalization

NOTE: Hospitalization signifies that the subject has been admitted to the hospital as an inpatient for any length of time. Treatment on an emergency, outpatient basis for an event not fulfilling any of the definitions of SAEs and not resulting in hospital admission does not qualify for this category, but may be appropriately included in category g (see below).

Complications that occur during hospitalization are usually AEs. If a complication prolongs hospitalization or fulfills any other serious criterion, the event will be considered as serious. When in doubt as to whether 'hospitalization' occurred, consult the Sponsor's Medical Monitor.

Hospitalization will not be considered an AE in and of itself. It will be considered an outcome of an AE. Therefore, if there is no associated AE, there is no SAE. For example, hospitalization for elective or pre-planned treatment of a pre-existing condition that did not worsen from baseline will not be considered an AE.

- Results in persistent or significant disability/incapacity

NOTE: The term disability means a substantial disruption of a person's ability to conduct normal life functions. This definition is not intended to include experiences of relatively minor medical significance, such as uncomplicated headache, nausea, vomiting, diarrhea, influenza, and accidental trauma (e.g., sprained ankle) that may temporarily interfere with or prevent everyday life functions but do not constitute a substantial disruption.

- Is a congenital anomaly/birth defect
- Is a suspected transmission of any infectious agent via a medicinal product
- Is an important medical event

NOTE: Medical and scientific judgment should be exercised in deciding whether expedited reporting as serious is appropriate in other situations; specifically, important medical events that may not be immediately life threatening or result in death or hospitalization but may jeopardize the subject or may require medical or surgical intervention to prevent 1 of the other outcomes listed in the above definition. These should usually be considered serious.

Examples of such events are invasive cancers, intensive treatment in an emergency room or at home for allergic bronchospasm, blood dyscrasias, or convulsions that do not result in hospitalization, or development of drug dependency or drug abuse. If in doubt as to whether

or not an event qualifies as an ‘important medical event,’ consult the Sponsor’s Medical Monitor.

#### **9.5.4.1.1.3 Non-Serious Adverse Event Definition**

AEs that do not result in any of the outcomes listed in [Section 0](#) are considered non-serious.

#### **9.5.4.1.1.4 Unexpected Adverse Event Definition**

An AE or suspected adverse reaction is considered unexpected if it is not listed in the Reference Safety Information section of the Investigator’s Brochure (for pegloticase) or US Prescribing Information (for MTX) or is not listed with the specificity or severity that has been observed. Unexpected, as used in this definition, also refers to AEs or suspected adverse reactions that are mentioned in the Reference Safety Information as occurring with a class of drugs or as anticipated from the pharmacological properties of the drug, but are not specifically mentioned as occurring with the particular drug under investigation.

#### **9.5.4.1.1.5 Adverse Events of Special Interest**

AEs of special interest include IRs, anaphylaxis, gout flares, and cardiovascular events. An external adjudication committee will adjudicate the AESIs of IR, anaphylaxis and cardiovascular events.

#### **Infusion Reaction**

An IR will be defined as any infusion-related AE or cluster of temporally-related AEs, not attributable to another cause, which occur during the pegloticase infusion and for up to 2 hours post infusion. Other AEs that occur outside of the 2-hour window following the infusion may also be categorized as an IR at the Principal Investigator’s discretion. Signs and symptoms of the IR and treatments administered will be documented in the medical record and in the eCRF, and will be adjudicated.

Examples of AEs not considered possible IRs include, but are not limited to: laboratory abnormalities that are unlikely to have occurred during or within 1 hour following the infusion (e.g., anemia), gout flares, most infectious diseases, or the recurrence or worsening of a known chronic medical problem identified in the subject’s medical history.

## **Anaphylaxis**

Any incidence of anaphylaxis should be reported as an SAE. Anaphylaxis will be defined using the National Institute of Allergy and Infectious Diseases/Food Allergy and Anaphylaxis Network criteria [Sampson et al, 2006], and will be adjudicated:

1. Acute onset of an illness (minutes to several hours) with involvement of the skin, mucosal tissue, or both (e.g., generalized hives; pruritus or flushing; urticaria, and angioedema (of lips, tongue, or uvula) and  $\geq 1$  of the following:
  - a. Respiratory compromise (e.g., dyspnea, wheeze-bronchospasm, stridor, reduced peak expiratory flow, hypoxemia)
  - b. Reduced blood pressure or associated symptoms of end-organ dysfunction (e.g., hypotonia [collapse], syncope, incontinence)
2. Two or more of the following that occur rapidly after exposure to a likely allergen for that subject (minutes to several hours):
  - a. Involvement of the skin-mucosal tissue (e.g., generalized hives, itch-flush, swollen lips-tongue, uvula)
  - b. Respiratory compromise (e.g., dyspnea, wheeze-bronchospasm, stridor, reduced peak expiratory flow, hypoxemia)
  - c. Reduced blood pressure or associated symptoms (e.g., hypotonia [collapse], syncope, incontinence)
  - d. Persistent gastrointestinal symptoms (e.g., crampy, abdominal pain, vomiting)
3. Reduced blood pressure after exposure to known allergen for that subject (minutes to several hours): systolic blood pressure  $<90$  mmHg or  $>30\%$  decrease from that subject's baseline.

## **Gout Flares**

It is common for potent urate-lowering therapies to lead to acute attacks of gout. Gout flares will be confirmed through questioning or direct observation detailed in [Section 9.5.4.8](#).

## **Cardiovascular Events**

Cardiovascular adverse events will be collected as part of the AE collection. External adjudication will be conducted for major adverse cardiovascular events (MACE) and congestive heart failure. Refer to the Adjudication Committee Charter for the detailed definition.

#### **9.5.4.1.2 Documentation of Adverse Events**

AE monitoring will begin from the signature of the ICF until the 6 month Post Treatment Follow-up Visit.

SAE monitoring will begin from the signature of the ICF until the 6 month Post Treatment Follow-up Visit.

ASG will conduct a search of Lost to Follow up subjects. If a subject is confirmed deceased, the SAE will be collected if the death occurred within 6 months post treatment.

Subjects will be questioned about AEs at each study visit, using nonspecific questions, such as “How have you been feeling since the last study visit?” AEs must be recorded on the AE eCRF and documented in the source record after the signing of the ICF.

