#### **9.3.3.1.1 Study considerations for subjects ending pegloticase infusions prior to 52 weeks**

- Methotrexate/placebo for MTX, along with folic acid, will be discontinued at the time of cessation of pegloticase infusions prior to Week 52.
- All subjects will complete the End of Pegloticase Infusions Visit and will remain on study through Week 52 regardless of whether they stop infusions due to sUA stopping rules or other reason (e.g. withdrawal of consent for pegloticase infusions).
- Subjects are encouraged to continue to participate in all visits through the end of the study. Subjects are especially encouraged to complete study visits at the study site during key efficacy and safety collections at Weeks 12, 14, 20, 21, 22, 23, 24, 32, 34, 36, 48, 50 and 52/End of Study/Early Termination, so that sUA labs and other key assessments can be completed. During visits between these key efficacy and safety collection visits, in subjects who have stopped infusions, subjects may complete study visits in person or via telephone to collect AEs, conmeds and gout flare information.
- Activities related to pre/post infusion monitoring or medication dispensation will not be completed once a subject has stopped pegloticase infusions. These activities include:
  - MTX/placebo for MTX compliance/reconciliation
  - Infusion reaction prophylaxis
  - IR prophylaxis compliance
  - Folic acid compliance
  - Pegloticase infusion
  - Pegloticase PK sampling
  - Pre-infusion MTX Polyglutamate sampling
  - MTX drug/dispensation related items
- Re-introduction of oral ULT's should not start until after the End of Pegloticase Visit laboratory tests are collected.

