#### Post Treatment Follow-up:

The intent is to obtain at least 6 months of follow-up on each subject after cessation of pegloticase infusions. If these 6 months occur prior to end of study at Week 52, such as in the case of a subject who ends pegloticase infusions on or before Week 24, there will be no follow-up visits after the Week 52/End of Study Visit. For subjects who end pegloticase infusions between Weeks 26 and 36, there will be at least 3 months of follow-up while the subject remains on-study prior to Week 52, and then one follow-up visit after the Week 52/End of Study Visit. For subjects who end pegloticase infusions between Weeks 38 and 52, there will be two follow-up visits at intervals of 3 months apart after the Week 52/End of Study Visit.

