#### **9.3.3.2 Removal of Subjects From Study**

In addition to completion of therapy and designated study visits through Week 52, the reason for discontinuation from the study should be recorded on the eCRF using 1 of the following categories:

- Lost to Follow-up. The subject does not return to the clinic for scheduled assessments, and does not respond to the site's attempts to contact the subject.
  - ASG (an external vendor that focuses on locating Lost to Follow-up subjects) will conduct a search of subjects whose status was determined "Lost to Follow-up" during the trial. This search for subjects whose status is "Lost to Follow-up" will be conducted throughout the study. See Section 9.5.4.1.2 for adverse event reporting if subject's status results in "Death."
    - For subjects whose status is determined to be deceased, their status previously considered to have been "Lost to Follow-up" may have the reason for discontinuation updated to "Death" if the Investigator deems appropriate. This will be considered on a case by case basis.
    - For subjects whose status is determined to be alive: Subjects categorization will remain "Lost to Follow-up".
- Withdrawal of Consent. The subject withdraws from the study. The clinical site should attempt to determine the underlying reason for the withdrawal and document it on the eCRF; (i.e. AE, voluntary withdraw) Specify.
- Study Terminated by Sponsor. The Sponsor, IRB, or regulatory agency terminates the study.
- Death

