#### **9.5.4.1.5 Reporting and Documenting SAEs and Product Complaints**

##### **9.5.4.1.5.1 Serious Adverse Events**

Any death, life-threatening event, or other SAE experienced by a subject during the course of the study, whether or not judged drug-related, must be reported within 24 hours of knowledge of the event by entering the information into the eCRF. If unable to access the eCRF, the event must be reported by submitting the completed SAE form via email or fax to the contact numbers provided below.

Fax [REDACTED]  
E-mail [REDACTED]

The event must be documented in source documentation and the eCRF. The following steps will be taken to report promptly and document accurately any SAE, whether or not it appears to be related to MTX/placebo for MTX and/or pegloticase:

1. Report the SAE to the Sponsor by entering the information into the eCRF within 24 hours after becoming aware that a subject has experienced an SAE. If unable to access the eCRF, the event must be reported by submitting the completed SAE form by email to [REDACTED] or fax within 24 hours after becoming aware that a subject has experienced an SAE.
2. Perform appropriate diagnostic tests and therapeutic measures, and submit all follow-up substantiating data, such as diagnostic test reports, hospital discharge summaries, and autopsy report to the Sponsor's representative.
3. Respond in a timely manner to any queries from Sponsor regarding the SAE.
4. Conduct appropriate consultation and follow-up evaluation until the SAE is resolved, stabilized, or otherwise explained by the Investigator.
5. Review each SAE report and evaluate the relationship of the SAE to MTX/placebo for MTX and/or pegloticase.
6. The Investigator must report all AEs or SAEs that meet the criteria for Unanticipated Problems Involving Risks to Human Subjects or Others to the IRB.

After receipt of the initial report, the information will be reviewed and the Investigator may be contacted with requests for additional information or for data clarification.

Follow-up will be obtained via the eCRF, fax, or e-mail, as necessary, until the event resolves or attains a stable outcome. Horizon or designee is responsible for the preparation of MedWatch 3500 A/Council for International Organizations of Medical Sciences I forms and analysis of similar events for individual occurrences (to be submitted as Investigational New Drug [IND] safety letters to the FDA and Investigators according to 21 CFR 312.32 by Horizon).

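### A death found by the lost-to-follow-up search is collected as an SAE only within 6 months of treatment, a window that closes before Week 52 for subjects whose last infusion was at or before Week 24

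*Protocol*

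**What the plan says.** Protocol 9.3.3.2 provides for an external vendor to search, throughout the study, for subjects classed as lost to follow-up. Protocol 9.5.4.1.2 then sets the limit for recording what the search finds: "If a subject is confirmed deceased, the SAE will be collected if the death occurred within 6 months post treatment". The same section gives the general rule: "SAE monitoring will begin from the signature of the ICF until the 6 month Post Treatment Follow-up Visit".

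Other current text sets a longer period for subjects who stop infusions early:

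- Protocol 9.3.3.1.1 says they "will remain on study through Week 52 regardless of whether they stop infusions due to sUA stopping rules or other reason". Between key visits, adverse events may be collected by telephone. Protocol 9.5.8.4 asks about adverse events again at Week 52.
- In the same section, methotrexate or its placebo "will be discontinued at the time of cessation of pegloticase infusions prior to Week 52", so the date of last treatment is close to the date of last infusion.
- The Post Treatment Follow-up text foresees that the 6 months may run out early ("If these 6 months occur prior to end of study at Week 52"), giving as its example a subject whose last infusion is at or before Week 24. For such subjects "there will be no follow-up visits after the Week 52/End of Study Visit".
- Protocol 9.5.4.1.5.1 requires 24-hour reporting of "Any death, life-threatening event, or other SAE experienced by a subject during the course of the study, whether or not judged drug-related", with no 6-month limit.

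Protocol 9.3.3.2 also says that a lost subject found to have died "may have the reason for discontinuation updated to" death. This depends on the Investigator's view of each case and carries no time limit.

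**The concern.** Two clocks apply to the same subjects. Observation of an early stopper runs to that subject's Week 52, but the SAE rule for a death found by the search runs from the end of treatment. Take two subjects who both stop at Week 8 and both die at Week 45. If one was still attending, the death is reported as an SAE. If the other had been lost and was then traced by the vendor, the death falls outside the 9.5.4.1.2 limit, although the sponsor knows of it and the subject's planned study period had not ended.

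At stake is whether known deaths over the planned 52 weeks are complete in the adverse event data. Early stopping is driven largely by the serum uric acid stopping rule. That rule also makes a subject a non-responder for the primary endpoint, so the shortened window falls on a group whose share is expected to differ by arm.

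**Working it through.** **Inputs.** Cut-off of 6 months post treatment (Protocol 9.5.4.1.2); planned observation to Week 52 (9.3.3.1.1); 90 and 45 subjects, with assumed Month 6 response of 71% and 43% (9.6.9); 145 subjects in total after enlargement (SAP 3.6). Assumptions: 6 months is 26 weeks, and the clock starts at the last infusion.

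**The plan's own figure.** The planning rates are used below, so the stated power was checked first, using a two-sided test at 0.05 with pooled variance under the null.

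- Mean rate = (45 × 0.43 + 90 × 0.71)/135 = 83.25/135 = 0.6167.
- Null SE = √(0.6167 × 0.3833 × (1/45 + 1/90)) = 0.0888.
- Alternative SE = √(0.43 × 0.57/45 + 0.71 × 0.29/90) = 0.0879.
- Power = Φ((0.28 − 1.96 × 0.0888)/0.0879) = 88.6%.

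This agrees with the stated 88%.

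**Uncovered time.** Weeks uncovered = 52 − (week of last infusion + 26).

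| Last infusion | Window ends (week) | Weeks uncovered before own Week 52 |
|---|---|---|
| Day 1 (week 0) | 26 | 26 |
| Week 2 | 28 | 24 |
| Week 8 | 34 | 18 |
| Week 16 | 42 | 10 |
| Week 22 | 48 | 4 |
| Week 24 | 50 | 2 |
| Week 26 | 52 | 0 |

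A subject with the last infusion at Week 50 is covered to about Week 76 (50 + 26). Under the stopping rule the earliest last infusion is Week 2, if high values at Weeks 2 and 4 are read before the Week 4 infusion. A last infusion on Day 1 would have another cause.

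**Size of the early-stopping pool.** Month 6 non-response is used as a rough stand-in for having stopped early. Expected number = n × (1 − response rate).

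- At 135: methotrexate 90 × 0.29 = 26.1; placebo 45 × 0.57 = 25.65.
- At 145, assuming 2:1: methotrexate 96.67 × 0.29 = 28.0; placebo 48.33 × 0.57 = 27.6.
- Ratio of shares, placebo to methotrexate: 0.57/0.29 = 1.97.

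The share is about double on placebo, and the count is about the same in both arms.

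**Subjects exposed to the gap.** Only those in the pool who are also lost to follow-up are affected. The documents give no loss rate. Assuming 2% to 20% of the pool, equal in both arms, the range at 135 is 0.5 to 5.2 methotrexate subjects (26.1 × 0.02 to 26.1 × 0.20) and 0.5 to 5.1 placebo subjects (25.65 × 0.02 to 25.65 × 0.20). These are subjects with a shortened window, not deaths. No death rate is given either.

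**Where such a death would have appeared.** SAP 11.3 ends treatment-emergent events 30 days after the last dose and puts later events in the follow-up period. That period has a summary of adverse events leading to death, and there is a listing of all such events. SAP 11.3.1 sends reported cardiovascular events to adjudication. A death not collected as an SAE would be missing from the summary and the listing, and a possible cardiovascular death would have no reported event for the committee to review.

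**The case against.** The strongest defence is that 6 months after treatment is the protocol's chosen safety horizon. It matches the general SAE window and the minimum follow-up after the last infusion, the Post Treatment Follow-up text accepts that it may end before Week 52, and it gives every lost subject the same time after drug. This explains the choice but does not remove the conflict. For retained early stoppers the protocol goes on collecting adverse events to Week 52, and 9.5.4.1.5.1 has no 6-month limit.

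Three stronger readings are tempting, and the documents do not support them.

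- A reader might infer that these deaths vanish from the record. The limit is on the SAE. Protocol 9.3.3.2 allows the discontinuation reason to become death, and SAP Section 7 summarises reasons for study discontinuation by randomized arm. That route is discretionary, however, and carries no SAE record or adjudication.
- A reader might infer that more placebo subjects are exposed. Under 2:1 allocation the expected numbers are nearly equal, and only the proportion is higher on placebo. Nor are 57% and 29% early-stopping rates. Some non-responders continue treatment (SAP 9.2.2 also counts subjects with too few measurements), and some subjects stop for other reasons, so the figures are not a strict upper bound.
- A reader might infer a distorted safety comparison. The treatment-emergent tables end 30 days after the last dose, before the 6-month limit comes into play.

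It is also fair to say that extending the window to Week 52 does not equalise coverage, since a completer would still be covered to about Week 76. The gain is completeness over the planned study period.

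**Conclusion.** The inconsistency is real and narrow. For a lost subject whose last infusion was at or before Week 24, Protocol 9.5.4.1.2 leaves 2 to about 26 weeks before that subject's Week 52 in which a known death is not collected as an SAE. Sections 9.3.3.1.1, 9.5.8.4 and 9.5.4.1.5.1 would capture the same death in a retained subject. The conclusion rests on taking 6 months as 26 weeks and on reading the post-treatment clock as starting at the last infusion.

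The number affected is probably small and cannot be derived from the documents; the range of about 0.5 to 5 per arm depends on an assumed loss rate. The effect is confined to follow-up-period adverse event summaries, the death listing and adjudication. This is a cheap improvement to the completeness of the safety record, not a threat to the trial's main comparisons.

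**What to change.** Reconcile Protocol 9.5.4.1.2 with 9.3.3.1.1 and 9.5.4.1.5.1 by changing the condition for deaths found by the search to: *the SAE will be collected if the death occurred on or before the later of the subject's planned Week 52 date and 6 months after the last dose of study drug*. The uncovered time before Week 52 is then zero for every subject.

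In the SAP, include these deaths by arm in the follow-up-period summary of adverse events leading to death, and keep the subject in the denominator. SAP 11.3 bases those percentages on subjects with follow-up beyond 30 days after the last dose, so a lost subject might otherwise be counted in the numerator only, or not at all.

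The cost is a protocol wording change, a matching line in the SAP, and a few extra SAE records that may have limited source information on cause. The search is already in place, and no visits are added.
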